#### Hypothesis:

$H_0: P_{iNO\ 75} = P_{Placebo}$  versus  $H_1: P_{iNO\ 75} < P_{Placebo}$  for at least one realization.

P: Proportions of patients undergoing heart-lung or lung transplantation from baseline to Week 18.

#### SAS code:

SAS code as below:

```

PROC FREQ DATA = DATA;
TABLES TREAT*PROSSTATUS*RESP / CMH NOPERCENT NOCOL;
WEIGHT FREQ;
RUN;

```

Total duration of hospitalization will be summarized by treatment arm and analysed using appropriate statistical test as part of exploratory analysis.

## 7.7 Safety Analysis

Adverse events (AEs and SAEs) and concomitant medication data will be analyzed and summarized based on Safety Analysis set.

### 7.7.1 Adverse Events:

The adverse events will be coded in accordance with Bellerophon standard procedures. The incidence of Treatment emerged adverse events (the percentage of subjects having experienced at least one AE) during a defined study period will be determined. Only adverse events with a start date on or after the date of randomization will be taken into account.

The following categories of adverse events will be compared between two treatment groups using Fisher's exact test.

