11.1.13.1. RHC Procedure

Hemodynamic stability will be established prior to recording baseline hemodynamic data and at Week 18 or early discontinuation in Part 1

Cardiac output (CO) will be determined by thermodilution (in triplicate). For each CO, PAP S/D/mean; SAP S/D/mean; mRAP; mPCWP or LVEDP, SpO₂, and mixed venous oxygen saturation (blood sample from tip of PA catheter when not in the wedge position) will also be measured. The average of the triplicate measurements will be used in the data analysis. The CO measurements must be within 15% of one another. To determine if the individual values are within 15% of one another, PAP S/D/mean; SAP S/D/mean; mRAP; mPCWP and LVEDP must be measured at end-expiration. All measurements will be recorded in the eCRF.

Important Note: The transducer must be leveled at the mid-axillary line at the level of the mid-sternum (half way between the mid-sternum and table top). The distance of the mid-axillary line from the table top must be recorded in the eCRF for the Baseline, Week 18, or any RHC performed at the time of study drug discontinuation. The transducer must be leveled to the same height at the baseline RHC and for all subsequent RHC.

Cardiac output must be performed only by thermodilution or Continuous Cardiac Output (CCO). Iced or room temperature saline may be used. The methods used for measurement should be maintained for all RHC and recorded in the eCRF.

Acute Vasoreactivity Testing

AVT will be performed after Baseline RHC measurements are completed and prior to randomization in all subjects at selected centers that will perform RHC in Part 1 if possible. AVT testing with iNO is preferred if available at the site. If not available, the site may use other means of AVT that are part of clinical care at the site. RHC must be performed as described in [Section 11.1.13.1](#). Measurements must be performed in triplicate after stabilizing the subject on oxygen at a flow rate to maintain SpO₂ at $\geq 90\%$ plus iNO 40 ppm for at least 5 minutes. Exposure RHC measurements will be recorded in the eCRF. Data recorded will include iNO dose (ppm) and duration of iNO exposure (minutes) or dose of alternative agent used for AVT and duration of exposure. A responder to AVT with iNO is defined as a decrease in mPAP by ≥ 10 mmHg to an absolute level of < 40 mmHg without a clinically significant decrease in CI.

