15.1. Definitions

15.1.1. Adverse Event

An AE is any untoward medical occurrence associated with the use of an investigational product in humans, whether or not considered investigational product related.

An AE can be any unfavorable or unintended sign (e.g., an abnormal laboratory finding), symptom, or disease temporally associated with the use of an investigational product, without any judgment about causality. This includes any events that occur during investigational product administration or, if present prior, have worsened in severity.

The Investigator will determine and record the seriousness, severity, relationship, and outcome for all AEs.

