15.4.1. Collection of Adverse Events and Serious Adverse Events

Any AE occurring prior to signing the ICF should be considered medical history or a pre-existing condition, and will be collected on the Medical History eCRF. Findings at Screening from physical exam, baseline laboratory results, etc. should also be considered medical history or pre-existing condition and be recorded accordingly.

At each visit, the Investigator will determine whether any AE has occurred and if it is related to the investigational product. Subjects will also be instructed to contact the site to report any AE that occurs between study visits. For randomized subjects, AEs and SAEs will be collected from signing of the ICF through the EOS and entered on the AE section of the eCRF.

SAEs (including those related to investigational product complaints/deficiencies) occurring from signing of the ICF through the EOS will be reported to Bellerophon Pulse Technologies Drug and Device Safety Department or their designee within 24 hours of an Investigator becoming aware of the event, using the AE/SAE page in the eCRF.

As laboratory abnormalities may fall into the category of expedited reporting, the Investigator will review the clinical laboratory test results in a timely fashion. Only those results qualifying as AEs/SAEs will be recorded in the AE section of the eCRF.

Adverse events will be coded according to the most current version of MedDRA in use. All medical device deficiencies associated with a SAE will be coded and reported as required.

For consented subjects who are screen failures prior to randomization, AEs will not be collected after the subject fails to qualify for randomization.

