16.4. Safety Analyses

Adverse events will be coded using the MedDRA dictionary. AEs (events that are new in onset or aggravated in severity following treatment) will be summarized under each dosing cohort, by

system organ class (SOC) and preferred term (PT). Comparisons between dosing cohorts will be made using Fisher's exact test for the proportion of subjects with a particular AE (grouped under one preferred term). Serious AEs (including death) will be summarized. In addition, AEs will be summarized by severity and relation to study drug.

Adverse events of special interest (AESI) include:

- Respiratory related AEs
- Epistaxis
- Syncope (new onset, or if history of syncope, recurrent syncope events)
- Clinically significant signs and/or symptoms (as determined by the Investigator) consistent with rebound PH (e.g., systemic hypotension, change in heart rate, new onset syncope, or decreased systemic oxygenation) temporally associated with acute withdrawal and including those associated with device malfunction or failure.

Other safety evaluations include:

1. Incidence of device malfunction and/or device failure leading to an AE
2. Incidence of rebound PH
3. Clinically significant changes in the following:
 - a. Clinical laboratory tests
 - b. Pulmonary function tests
 - c. Vital signs

All safety data will be summarized by treatment groups with descriptive statistics or frequency table.

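### SAP 7.7.1 selects treatment-emergent adverse events by start date alone, contrary to protocol 16.4, so an event that begins between consent and randomisation and worsens on study drug can drop out of the between-arm tables

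*SAP*

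**What the plan says.** SAP 7.7.1 names its outcome as treatment-emergent events: "The incidence of Treatment emerged adverse events (the percentage of subjects having experienced at least one AE) during a defined study period will be determined". It then gives one selection rule: "Only adverse events with a start date on or after the date of randomization will be taken into account". The rule has no clause for worsening and does not refer to the first dose or to time of day. The SAP defines the term nowhere else; TEAE otherwise appears only in its abbreviation list.

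Protocol 16.4 sets a different scope: "AEs (events that are new in onset or aggravated in severity following treatment) will be summarized under each dosing cohort". The general definition in protocol 15.1.1 agrees with it: "This includes any events that occur during investigational product administration or, if present prior, have worsened in severity".

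On collection, protocol 15.4.1 says that for randomised subjects "AEs and SAEs will be collected from signing of the ICF through the EOS". The same section assigns anything before consent, and findings at Screening, to medical history. The Part 1 schedule (protocol Table 2) allows Week 0 up to 28 days after the screening visit. Protocol 13.1 starts study drug after randomisation, during the same visit.

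SAP 7.7.1 also provides for a per-patient listing of all adverse events and a separate presentation of screening events for enrolled patients. SAP section 11 is blank, and the SAP change history does not mention the adverse-event rule.

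**The concern.** The two documents give different answers to the question of which events enter the safety tables, and the SAP is the one that will be programmed. An event recorded after consent, still present at the first dose and then more severe on study drug meets the protocol's definition but fails the SAP's date test.

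The events of special interest in protocol 15.1.5 include dyspnoea, cough, hypoxia, bronchitis and syncope. Protocol Table 6 lists most of these as common in this population without any exposure to study drug, so worsening is one plausible form that a drug effect could take. SAP section 2.0 reports 9 serious events at 75 mcg/kg IBW/hr in the Phase 2 trial against 4 in each of the other two groups, and attributes the excess adverse events to the respiratory system. Protocol 5.1 describes the same serious events as balanced. With that history, the counting rule for respiratory events should be free of ambiguity.

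There is a lesser issue in the other direction. A rule that uses only the date also admits events from earlier on the randomisation day, before any study drug was given.

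**Working it through.** The plan gives no figure that depends on this rule, so there is nothing to recompute. The check is to apply both definitions to each possible timing of an event.

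| Event | Protocol 16.4 | SAP 7.7.1 |
|---|---|---|
| 1. Present before consent, unchanged on drug | Not counted (medical history) | Not counted |
| 2. Present before consent, worsens on drug | Counted | Probably counted, if entered as a new event dated at the worsening |
| 3. Starts between consent and randomisation, unchanged | Not counted | Not counted |
| 4. Starts between consent and randomisation, worsens on drug, worsening entered as a new line | Counted | Counted |
| 5. As 4, but kept as one record with its original start date | Counted | **Excluded** |
| 6. Starts on the randomisation date before the first dose, no later worsening | Not counted (does not follow treatment) | **Included** |
| 7. Starts after the first dose | Counted | Counted |

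The definitions disagree in rows 5 and 6 only.

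**Row 5.** Four conditions must hold together: onset between consent and randomisation (a window of up to about 28 days, taking consent at the screening visit), still ongoing at the first dose, more severe on drug, and held as a single record. Protocol 11.1.17.1, 15 and 15.4.3 ask for severity, dates and outcome for each event. They do not say whether a worsening opens a new line. Excluding such a record can only lower a count. It removes the subject from a given incidence only if the subject has no other qualifying event in that category. If the worsening is caused by the drug, the difference between arms is understated; if not, both arms lose events.

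**Row 6.** This needs a pre-dose event on the calendar date of randomisation. The clearest source is the catheterisation substudy of about 50 subjects, where protocol 11.1.13.1 says "AVT will be performed after Baseline RHC measurements are completed and prior to randomization". The protocol fixes only the order of these procedures, not that they share a date with randomisation, and SAP Table 17 gives Baseline a range of day 1 or earlier. If the procedure is on an earlier day, its events fail the SAP rule and the problem does not arise. An event that precedes randomisation cannot depend on the assigned arm.

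**The case against.** The strongest reply is that the gap is narrow and that ordinary recording practice may close it. Under protocol 15.1.1 the worsening of a prior condition is itself the adverse event, so its natural onset is the date of worsening, which passes the SAP rule. Chronic respiratory symptoms present before consent are medical history and would take this route. A reader might therefore infer from the SAP rule that the respiratory signal as a whole is suppressed. The documents do not support that.

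The pool for row 5 is also thin. Adverse-event assessment is first scheduled at Baseline (protocol Table 2 and 11.1.17), although 15.4.1 starts collection at consent, and clinical worsening during Screening or Run-in bars entry to the treatment phase (protocol 9.4). Whether worsening becomes a new line may be settled in the eCRF completion guidelines that protocol 19.1 cites, which are not among the documents. Nor would these events vanish, since SAP 7.7.1 keeps the listings and the screening presentation.

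All of this limits the size of the problem and is accepted. It does not remove the contradiction. Neither document states a recording convention, and neither the listings nor the screening presentation puts on-drug worsening back into the Fisher's exact comparisons or the summary tables.

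A reader might also infer that catheterisation and vasoreactivity events are certain to be counted as treatment-emergent. That too goes beyond the text. It depends on a same-day procedure, vasoreactivity testing is done only where possible, and no bias between arms would follow.

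**Conclusion.** The point holds as a contradiction between the SAP's counting rule and protocol 16.4 that the SAP does not declare. Its consequence is limited to events that start between consent and randomisation, worsen on study drug and keep their original start date. These would be missing from the between-arm comparisons and from the event, severity and special-interest tables. The same-day inclusion is minor and conditional.

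The number of affected events cannot be derived from the documents, and no effect on a conclusion has been shown. The primary efficacy analysis is not touched. The change should still be made before unblinding, because it is cheap and every treatment-emergent table in SAP 7.7.1 uses the rule.

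This rests on two assumptions: that no convention outside these documents already turns each worsening into a new dated record, and that the SAP rule will be programmed as written.

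**What to change.** In SAP 7.7.1, define a treatment-emergent adverse event as one with onset, or an increase in severity, at or after the first dose of study drug, in line with protocol 16.4. Then:

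- State that a worsening is recorded as a new adverse-event line or as a dated change in severity.
- For events on the date of the first dose, use onset time or a flag for before or after the first dose. Protocol 11.1.15 has the Week 0 start supervised, with vital signs every 15 minutes, which makes this practical. It does not say that the dosing start time is captured, so confirm that it is.
- Apply the definition to all treatment-emergent tables and comparisons in 7.7.1. Leave the separate screening presentation as it is.

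If the date rule is kept on purpose, list it in SAP section 11 with the reason.

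The cost is SAP wording, programming of the event flag and possibly one eCRF instruction. No visit or assessment changes.

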**From Date of Randomization through End of double blind period (Week 18):**

- All events through end of blinded period (week 18),
- All events at Body System Organ class level through end of blinded period (week 18),
- All events at preferred term level through end of blinded period (week 18).

Comparison between groups of the incidence of serious adverse and the incidence of death (if any) will be done by Fisher's exact for the treatment period and the entire study through post treatment follow-up.

All AEs will be listed for each patient and summarized by formula groups according to the System Organ Class (SOC) and Preferred Term (PT) assigned to the event using MedDRA. All the summary tables will be presented from randomization through end of treatment for blinded phase of study and from randomization through end of follow-up period.

The following will be summarized for subjects in safety analysis set:

- Adverse events in any category - patient level
- Adverse events in any category - episode level
- Adverse events by system organ class and Preferred Term
- Adverse events by SOC and PT presented by maximum reported severity
- Adverse events related to study product, presented by SOC and PT
- Adverse events leading to withdrawal of study product, presented by PT, arranged by SOC
- Adverse events causality related to study product, presented by SOC and PT
- Adverse events leading to study product interruption, presented by PT, arranged by SOC
- Adverse events leading to dose reduction of study product, presented by PT, arranged by SOC
- Adverse events leading to increase in dose of study product, presented by PT, arranged by SOC
- Adverse events leading to discontinuation of study product, presented by PT, arranged by SOC
- Key information for serious adverse events
- Serious adverse events causality related to study product, presented by SOC and PT
- Serious adverse events leading to study product interruption, presented by PT, arranged by SOC
- AE's on special interest

AE/SAE data collected at screening will be presented for all enrolled patients separately.

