25. Any subject who has been enrolled in any previous clinical study with inhaled NO administered through pulse delivery.

Additional Criteria to Continue to Treatment Phase from Run-in period (Week 0 to Week 2)

1. Subjects must demonstrate an average daily usage of the INOpulse device of ≥ 12 hours (rounded to the nearest hour), with no more than 2 days of usage < 8 hours per day, during the initial 2 weeks of study.
2. If a subject experiences clinical worsening during the Screening or Run-in period, the subject will not be eligible to enter into the treatment phase of the study.
3. Subjects who have been randomized at baseline and found not to meet all Inclusion criteria and/or who meet Exclusion criteria during the Run-in period will be withdrawn from the study. These subjects will be replaced to meet total target enrollment.

Part 2 Open Label Period: Diagnosis and main criteria for inclusion and exclusion:

Inclusion Criteria Part 2:

1. Informed Consent Form prior to the initiation of any study mandated procedures or assessments
2. Subject must have completed 18 weeks of blinded therapy and all assessments at week 18
3. In the opinion of the Investigator, open label treatment is in the best interest of the subject after 18 weeks of blinded treatment is completed

Exclusion Criteria Part 2 Open Label Period:

1. Subject has initiated therapy with Riociguat

Investigational product, dosage and mode of administration:

Part 1 Blinded Treatment Period:

In a randomized, double-blind manner, all subjects randomized to iNO at a dose setting of 75 mcg/kg IBW/hr will be treated by means of an INOpulse delivery device and product-specific cannula. The active study drug, nitric oxide for inhalation (iNO), will be provided in size 0.074 liter aluminum cartridge at a concentration of 6.0 mg/L (4880 ppm). All subjects will change cartridges approximately every 12 hours.

All subjects randomized to receive iNO will receive 15 mcg/kg IBW/hr for the first 2 weeks (Run-in phase) followed by iNO at 75 mcg/kg IBW/hr for 16 weeks.

Part 2 Open Label Period:

All subjects enrolled in Part 2 Open label treatment will receive iNO at 75 mcg/kg IBW/hr.

Duration of treatment:

Part 1 Blinded Treatment Period:

Until the subject has completed 18 weeks of blinded treatment

Part 2 Open Label Period:

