Subjects will remain in the study and continue to receive blinded treatment according to their randomization for an additional 16 weeks for a total of 18 weeks.

Part 2-Open Label Period -Subjects will be offered open label therapy when a subject completes 18 weeks of blinded drug therapy.

Subjects will be given the opportunity continue in Part 2 Open Label Treatment and will receive iNO at 75 mcg/kg IBW/hr with the INOpulse delivery device until the drug-device investigational product is approved and available as a marketed product or the Sponsor decides to discontinue development of iNO for PAH.

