## 5.0 Study Design

### 5.1 General Design and Plan

[figure not shown]
This is a multi-center, randomized, double-blind, placebo-controlled, parallel-group design to determine the efficacy, safety and tolerability of pulsed iNO versus placebo in symptomatic subjects with PAH currently receiving background PAH medication and LTOT.

The study consists of two parts Part 1, the Blinded Treatment Period, and Part 2, the Open Label Extension Period. The duration of treatment in double blind period will be a maximum of 18 weeks. Subjects will be offered open label therapy when a subject completes 18 weeks of blinded drug therapy.

Screen failures will be defined as subjects who sign the ICF but fail to meet the eligibility criteria and/or do not qualify for randomization.

Subjects who do not complete their scheduled visits, have not died, and have not officially withdrawn from the study are considered lost to follow-up.

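### The second between-group Fisher test of SAEs and deaths (SAP 7.7.1) appears to take in open-label time, when former placebo subjects are also on iNO, and so is diluted towards no difference

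*SAP*

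**What the plan says.** In SAP 7.7.1, under the subheading for randomization to Week 18, Fisher tests of all adverse events (overall, by system organ class and by preferred term) stop at the end of the blinded period. The next sentence treats SAEs and deaths differently. Their comparison is to be made by Fisher's exact test "for the treatment period and the entire study through post treatment follow-up". The summary tables are likewise to run "from randomization through end of treatment for blinded phase of study and from randomization through end of follow-up period".

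On what the study is, SAP 5.1 states: "The study consists of two parts Part 1, the Blinded Treatment Period, and Part 2, the Open Label Extension Period". On treatment in Part 2, the Protocol synopsis states: "All subjects enrolled in Part 2 Open label treatment will receive iNO at 75 mcg/kg IBW/hr". Table 1 in both documents shows the placebo cohort moving to iNO. The synopsis ties the end of Part 2 to marketing approval or a sponsor decision, so follow-up has no fixed length.

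SAP 7.1.6 groups safety subjects by treatment received and does not say where a placebo subject belongs after switching. SAP 9.0 gives Part II its own copy of the adverse-event tables. Protocol 16.4 asks for Fisher tests between dosing cohorts without naming a period.

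**The concern.** A between-group safety test is informative only while the groups receive different treatments. After Week 18 every continuing subject is on iNO, so added time brings events to both groups at what is presumably the same rate. The two cumulative proportions rise together and their ratio moves towards 1.

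Two further defects follow from the same wording:

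- **Exposure.** Fisher's test counts subjects, not time at risk. With an open-ended Part 2, early enrollees accrue far more follow-up than late ones. Only Part 1 completers may enter, so any arm difference in discontinuation also produces unequal follow-up.
- **Grouping.** Under grouping by treatment received, a switcher could stay with placebo, move to iNO, or contribute to both groups. Each choice gives a different test.

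At stake is how a blinded-period imbalance would be read. SAP 2.0 reports 9 SAEs on the 75 mcg/kg IBW/hr dose against 4 on placebo in Phase 2, with the excess in the respiratory system. Protocol 5.1 calls the same SAEs balanced across cohorts. With that history unsettled, the plan should not create a second p-value that tends towards no difference by construction.

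**Working it through.** **Does the second window reach into Part 2?** Neither document defines the entire-study window or its follow-up.

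- Neither schedule of assessments contains a post-treatment visit. Part 2 Week 0 is done at Part 1 Week 18, and subjects who stop drug are followed to Week 18 (Protocol 10.1 and 11). Apart from a vital-status check 30 days after lung transplantation (Protocol 11.1.25), the scheduled contact after Week 18 is Part 2.
- The tables sentence contrasts the end of blinded treatment with a window "from randomization through end of follow-up period", so the second window appears to extend past the blinded phase.

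Pooling Part 2 is therefore an inference, but a well-supported one.

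**The plan's own figure.** SAP 5.4 plans 188 randomized to give 150 with 20% dropout: 150 / 0.8 = 187.5, rounded up to 188, or 94 per arm. This reproduces. The plan states no event rate or power for safety tests.

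**Inputs for the illustration**

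- Group size: 94 per arm (SAP 5.4).
- Entry to Part 2: about 150 of 188 (Protocol 12.3, Table 5), 150 / 188 = 80%. 100% entry is shown as a check.
- Open-label time: 16, 52 and 104 weeks, assumed as a range.
- SAE risk per 18 weeks: 80 Phase 2 subjects randomized 1:1:1 is about 27 per arm; 4/27 = 15% and 9/27 = 33%. This treats event counts over 16 weeks as subjects with an event over 18 weeks, which is an assumption. A second assumed pair is 10% and 20%.
- Test level: two-sided 0.05, assumed, because none is stated for these tests.
- Switchers stay in their original group. Hazards are constant, and both groups have the iNO hazard in Part 2. Non-entrants contribute to Week 18 only.

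**Formulas.** With 18-week risks p0 (placebo) and p1 (iNO), entry share e and t open-label weeks:

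- hazard on iNO: h = −ln(1 − p1) / 18
- probability of staying event-free after Week 18: S = (1 − e) + e × exp(−h t)
- cumulative risks: 1 − (1 − p0) S and 1 − (1 − p1) S
- risk difference: (p1 − p0) S

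The absolute difference is thus multiplied by S, which is below 1, while both risks rise.

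**Worked case: 15% vs 33%, e = 0.8, t = 52**

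- h = −ln(0.67) / 18 = 0.02225
- exp(−0.02225 × 52) = 0.314
- S = 0.2 + 0.8 × 0.314 = 0.452
- Placebo risk: 1 − 0.85 × 0.452 = 61.6%. iNO risk: 1 − 0.67 × 0.452 = 69.7%.
- The difference falls from 18 points to 0.18 × 0.452 = 8.1 points, and the risk ratio from 2.2 to 1.13.

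**Exact Fisher power, 94 per arm, 15% vs 33%**

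| Open-label weeks | Risks, 80% enter | Risk ratio, 80% enter | Power, 80% enter | Power, all enter |
|---|---|---|---|---|
| 0 (blinded only) | 15% vs 33% | 2.20 | 79% | 79% |
| 16 | 35.4% vs 49.1% | 1.39 | 41% | 35% |
| 52 | 61.6% vs 69.7% | 1.13 | 18% | 11% |
| 104 | 76.3% vs 81.3% | 1.07 | 10% | 4% |

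With 10% vs 20% and 80% entry, power is 41% in the blinded period, then 21%, 10% and 7%. With assumed deaths of 2% vs 6% it is 15%, then 10%, 7% and 5%. The direction is the same at every rate tried.

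**The case against.** A reader might infer that the plan hides a safety difference. The documents do not support that. The same sentence also orders a treatment-period test, the all-event tests stop at Week 18, blinded-phase tables are produced, and Part II is tabulated separately. A blinded-period excess would be tested and shown whatever the second test gave. No decision rests on the second p-value either: it has no stated threshold, and SAP 8.0 leaves safety stopping to the DMC's medical judgement.

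A narrower reading of the second window is also possible. The sentence sits under a subheading that ends at Week 18, and subjects who stop drug are encouraged to continue assessments to Week 18. The two windows might mean on-drug time, and on-drug plus off-drug time within Part 1. That reading fits poorly with the tables sentence and with the SAP's definition of the study, but it cannot be excluded. It has one practical consequence: simply deleting the second window could remove the only comparison that counts SAEs and deaths occurring off drug before Week 18.

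A reader might also take this to be a comparison by randomized arm. SAP 7.1.6 says treatment received, so the gap is the missing rule for switchers.

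Finally, the Phase 2 rates are fragile. They are event counts, and the Protocol's description of them disagrees with the SAP's. The power figures are therefore illustrations, not forecasts.

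**Conclusion.** The point holds in a limited form. Read literally, the second Fisher test of SAEs and deaths includes time when both groups are on iNO, is diluted towards no difference, ignores exposure, and cannot be programmed unambiguously. It adds a misleading comparison beside a sound one and does not replace it.

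Under the assumptions above, one year of open-label follow-up reduces power from 79% to between 11% and 18% for 15% vs 33%, and from 41% to between 8% and 10% for 10% vs 20%. The lower end assumes all enter Part 2; the upper end assumes 80% do. The dilution itself depends on both groups sharing a similar event rate in Part 2, not on the particular rates chosen. If the sponsor meant a narrower window, the dilution does not arise, but the sentence still needs a definition. The change should be made, as it is specific and nearly free.

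**What to change.** Replace the sentence in SAP 7.7.1 with wording such as:

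> Between-group Fisher tests of SAEs and deaths are limited to events from randomization through Week 18, on or off study drug. Part 2 events are summarized descriptively, separately for iNO-to-iNO and placebo-to-iNO subjects, with exposure-adjusted rates.

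This sets the window explicitly, which matters because Table 1 of the SAP labels only Weeks 3 to 18 as the treatment period, while 7.7.1 counts from randomization. It retains off-drug events before Week 18 and settles where switchers are reported. Any cumulative table through the end of follow-up should carry the same split by prior arm, without a between-group p-value. SAP 9.0 should point to this split when it replicates the Part I tables.

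The cost is SAP wording and table shells. No data collection, sample size or primary analysis changes.
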